Effect of Low-pressure Pneumoperitoneum on Pain and Inflammation Post Laparoscopic Cholecystectomy: A Randomized, Double-blinded, Controlled, Clinical Trial.

ClinicalTrials.gov Identifier: **not yet assigned**

Date protocol accepted by IRB at the University of Jordan: **15th January 2020**

Study Summary:

In the era of laparoscopic abdominal surgeries, pneumoperitoneum pressure is set to a point of 12-15 mmHg. The new generation of surgeon has been questioning if we could do laparoscopic surgeries with no compromise at a lower pneumoperitoneum pressure in the aim of improving the quality of patients' lives postoperatively and efficacy of health care system. In reviewing the literature, such intervention has showed benefit in terms of decreasing postoperative pain (1) and rise of inflammatory markers (2). This study is designed as a randomized double- blinded controlled clinical trial to challenge such hypothesis. The study shall be conducted on patients at The University of Jordan hospital booked electively for laparoscopic cholecystectomy then randomized into two groups operated at either standard or low pneumoperitoneum pressure then assessed post operatively for pain and rise of inflammatory markers.

Research design:

It is a clinical trial, designed to look for a statistical difference in pain and rise of inflammatory markers post operatively between interventional group which is operated at a low-pressure pneumoperitoneum of 8-10 mmHg compared to the standard of care of pneumoperitoneum set at a pressure of 12-14 mmHg.

further to increase validity of results and strengthen the study design, the study participants are randomized, the groups are masked, and the data is blinded to investigators, analyst, and participants.

Research subjects:

All patients admitted to surgery ward through clinic with the diagnosis of multiple gallbladder stones undergoing laparoscopic cholecystectomy are to be considered for enrollment in this study.

Inclusion criteria:

- Elective admission for laparoscopic cholecystectomy
- Minimum age of 12 years
- American Society of Anesthesiologists (ASA) score 1 or 2

Exclusion criteria:

- Current or previous diagnosis of acute cholecystitis confirmed by ultrasound.
- previous GI surgeries, except bariatric and anti-reflux surgeries
- Currently on immunosuppressant agents
- Pregnancy
- Breastfeeding
- Currently diagnosed with drug addiction
- American Society of Anesthesiologists (ASA) score 3, 4, 5, or emergency surgery

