Post-operative after hospital discharge the following are to be collected: pain score out of 10 according to patient perception recorded on 7th day post-op and to be collected via phone call, post-operative complications up to day 30 (readmission, CBD stone, pancreatitis, cholangitis, ..etc.), and histopathology result.

The following inflammatory markers are to be investigated: white blood cell count, platelet count, erythrocyte sedimentation rate, C reactive protein level, albumin level, free serum cortisol level, interleukin-6 level, interleukin-17 level, interleukin-1 beta level, tumor necrosis factor alpha level.

Flow of study work:

After ensuring patients eligibility for study and obtaining informed consent, they are to be allocated to one of study arms randomly. Observations are to be taken and entered to on-line excel. After discharge patients are to be followed on day 7 post-op to collect pain score via phone call, complications are to be followed up to day 30 post-op from electronic records.

Regarding inflammatory markers, the tests are to be performed at Jordan University Hospital laboratories, the blood samples are to be collected safely by study assistants and delivered to the lab labeled with patient name, MRM, date, and time of collection. The runoff tests are done as standardizes by hospital laboratory policies.

Specifications to operation:

Patients enrolled in the study are to undergo laparoscopic cholecystectomy as per the following protocol:

- Regarding general anesthesia, the use of dexamethasone during induction is to be avoided
- Regarding creation of pneumoperitoneum, the choice is given to operating surgeon to choose either open, closed, or optical technique
- Regarding number and site of trocars, the choice is given to operating surgeon to perform as per trained
- Cholecystectomy is to be performed as standardized, after establishment of critical view of safety, the operating surgeon is to carry on steps to establish hemostasis, clipping of cystic duct, and dissection of gallbladder from its liver bed
- Retrieval of specimen is to be done through umbilical port
- The use of endoclose device for closure of fascia is to be avoided
- The infiltration of local anesthesia at site of trocars is to be avoided
- Regarding skin closure, the choice is given to operating surgeon to perform as per trained

Data management and analysis:

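### Complications after discharge are sought only in electronic records, and the day-7 call is described as asking only about pain, so post-discharge complication rates in both arms can only err downward

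*Protocol*

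**What the plan says.** The post-discharge part of the protocol's Observations section lists three items. The first is "pain score out of 10 according to patient perception recorded on 7th day post-op and to be collected via phone call". The other two are "post-operative complications up to day 30 (readmission, CBD stone, pancreatitis, cholangitis, ..etc.), and histopathology result".

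Flow of study work then assigns the sources. The phone call appears again with the same content, and complications follow in the same sentence: "After discharge patients are to be followed on day 7 post-op to collect pain score via phone call, complications are to be followed up to". The source given there for complications is a different one: "complications are to be followed up to day 30 post-op from electronic records".

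Neither the protocol nor the SAP describes a clinic visit, a day-30 call, complication questions for the patient, or a request for records from other providers. The trial runs at a single hospital (Study Summary: "The study shall be conducted on patients at The University of Jordan hospital booked electively for laparoscopic cholecystectomy"), and the electronic records are not identified further. No rule separates a patient with no event from a patient about whom nothing is known. The SAP plans no analysis of complications and has no missing-data rule.

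**The concern.** A record search finds only events that reach the record. A patient who has a problem after discharge and is treated at home, or by a provider outside the system searched, leaves no trace in it. With no other source of information, such a patient looks the same as one who recovered without incident. The last planned study contact is on day 7, which is 30 − 7 = 23 days before the window closes, and even that contact is not described as asking about complications.

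What is at stake is the descriptive complication rate after discharge. Counts in arms of 50 are likely to be small, so a few missed events could change the impression they give, and a zero or very low count would look more reassuring than it should. The staff already plan to telephone every patient, so most of the means to reduce the gap are in place.

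**Working it through.** **Plan's own figure.** The only relevant number is the sample size, a convenience sample of 100, or 100 / 2 = 50 per arm (Protocol, Sample size). The documents give no complication rate, effect size, power or capture rate, so there is nothing further to reproduce. Everything below except the 50 per arm is an assumption for illustration.

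**Model.** Let *s* be the share of post-discharge events that reach the records, with no false positives. Events in the index stay happen in the study hospital and should be in its own records, and intraoperative complications are recorded directly, so *s* applies only after discharge:

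observed rate = in-hospital rate + *s* × post-discharge rate.

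Since *s* cannot exceed 1, the observed rate cannot exceed the true rate.

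**Effect on the comparison when *s* is equal in both arms** (post-discharge true rates p1 and p2):

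- Relative risk: (*s* × p1) / (*s* × p2) = p1 / p2, unchanged.
- Risk difference: *s* × (p1 − p2), shrunk by the factor *s*. An assumed true difference of 6 points would appear as 6 × 0.8 = 4.8, 6 × 0.7 = 4.2 or 6 × 0.5 = 3.0 points.

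**Effect on a zero count.** With 0 of 50 seen, the one-sided 95% upper limit for the observable rate is 1 − 0.05^(1/50) = 5.8%. The limit for the true post-discharge rate is that value divided by *s*. The chance of seeing no event in an arm of 50, at an assumed true post-discharge rate of 5%, is (1 − 0.05 × *s*)^50.

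| Assumed capture *s* | Upper limit for true rate, 0 of 50 seen | Chance of 0 of 50 at a true rate of 5% |
|---|---|---|
| 1.0 | 5.8% | 7.7% |
| 0.8 | 5.8 / 0.8 = 7.3% | not computed |
| 0.7 | 5.8 / 0.7 = 8.3% | 16.8% |
| 0.5 | 5.8 / 0.5 = 11.6% | 28.2% |

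**Would full capture make the comparison informative?** For assumed true rates of 5% and 15%, two-sided power at 50 per arm and alpha 0.05 is 38% at full capture, 28% at *s* = 0.7 and 21% at *s* = 0.5. It is low in every case, so better capture mainly improves the description of harm.

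**The case against.** The strongest reply is that complications are not what this trial sets out to compare. The title and Research design give the aim as pain and inflammatory markers, and the SAP plans no complication test. That stands, and it limits how much this point weighs.

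Three stronger readings are tempting, and the documents do not support them.

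- A reader might infer that the trial is meant to establish safety, because the Study Summary asks "if we could do laparoscopic surgeries with no compromise at a lower pneumoperitoneum pressure". That phrase is background on what surgeons have been asking. No safety, equivalence or non-inferiority claim is planned.
- A reader might infer that missed events will be entered as complication-free. Neither document contains a coding rule. This is the likely result of a record search with no other input, but it is not written down. Nor can the reach of the records be known: a system shared between hospitals would narrow the gap, although events managed at home would still be missed.
- A reader might infer that the gap favours low pressure. Nothing suggests this. The same source serves both arms and participants are masked. If capture is equal, the relative risk is preserved.

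Two further limits stand. Routine surgical follow-up is neither described nor excluded, so day 7 is the last planned study contact and not necessarily the last clinical one. The SAP is also written in the past tense, so new calls may no longer be possible.

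None of this supplies a second route for finding post-discharge events, so the downward direction of the error remains.

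**Conclusion.** The point holds as a modest design weakness that should be corrected. Followed as written, the plan can only undercount complications between discharge and day 30, in both arms, and can only shrink an absolute difference if capture is equal. The intraoperative data are collected separately and are unaffected.

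The direction rests on the text and on the absence of false positives. The size is unknown, because the documents give neither the coverage of the records nor the share of patients who seek care elsewhere. The range of 7.3% to 11.6%, against 5.8% at full capture, depends on three assumptions: capture of 80% to 50%, zero observed events in an arm of 50, and application to post-discharge events alone.

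**What to change.** - **Day-7 call.** Add a short fixed set of questions: any readmission, emergency visit or clinic visit at any hospital, and any new symptoms or treatment since discharge. Use the electronic records to confirm and date what is reported.
- **Days 8 to 30.** Either repeat the same questions in a brief day-30 call by the same staff, or report the outcome as complications found in the record system, which should be named with its coverage. The call is optional, because it is a larger step than the day-7 questions.
- **Coding.** Enter patients who are not reached and have no record as unknown, and report by arm how many have complete information to day 30.
- **If data collection is over.** Label the outcome by its source and apply the coding rule. This needs no new data.

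**Cost.** The day-7 questions add a few minutes to a call already planned for every patient. The optional day-30 step adds up to 100 short calls, plus repeat attempts and the checking of reported events against records. No extra visit or procedure is needed. The reported complication rate may come out slightly higher.

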Analysis was conducted using SPSS version 1.0.0.1406. Gender, smoking status, ASA score, and difficulty of surgery were analyzed using Chi-square cross table. Mean duration of total operative time, insufflation time, and mean hospital-stay were analyzed using Student's 2-tailed t-test. The mean intensity of pain was analyzed using Mann-Whitney U test. Inflammatory markers (WBC, Plt, ESR, CRP, Albumin, Cortisol, IL-6, IL-17, TNF- α , IL-1 β) levels were analyzed using Welch's t-test. Subgroup analysis for the inflammatory markers was done to eliminate the effect of dexamethasone given by anesthesia team at the time of anesthesia induction, analysis was done using Welch's t-test. All test set *p*-value was set at 0.05 to consider results significant.

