Allocation to groups:

participants are to be given numbers in study and be labeled with it. A preset computer-generated list is to be used to divide patients between two study arms into either of masked groups. Allocation to groups is random according to the computer-generated randomized list.

Masking (blinding) method:

The two study arms are to be color coded. The codes are to be used for randomization, data entry and analysis. None of the participants, investigators and analyst are to be informed of color code reference. the principal investigator, operating surgeon and circulating nurse during operation are to be informed of the color code meaning. After closure of the study, the color codes can be disclosed to the public.

Criteria to discontinuation:

Any participant withdrawing consent during any time of the study.

Patients found to have intra operative adhesions and evidence of previous inflammation are not to be discontinued from the study.

Sample size:

A convenient sample of 100 participants is decided, divided into 50 for each study group.

Intervention:

Interventional group is to be operated at low-pressure pneumoperitoneum which is set at 8-10. Control group is to be operated at standard-pressure pneumoperitoneum which is set at 12-14. The pressure set point is to be determined at the beginning of surgery, any change to pressure after initial insufflation is not to change the participants study arm grouping.

Observations:

Pre-operative demographics are to be collected for each patient, including patient name, medical record number (MRM), age, gender, weight, height, ASA score, medical history, surgical history, current medications, marital status, smoking status, operation date.

During operation, the following are to be observed and recorded: time of surgery start, time of surgery end, total time of insufflation, method of insufflation (open, closed), operator level of experience, intraoperative findings (adhesions, inflammation, perforation, bile leak), difficulty of surgery subjectively assessed by operator (easy, moderate, difficult), estimated blood loss, change of pneumoperitoneum pressure set point, intraoperative mortality, intraoperative complications.

Post-operative during hospital-stay the following are to be collected: pain score out of 10 according to patient perception recorded at 6hr, 12hr and 24hr post-op, hospital stay length in days, total analgesia given post-op (number of dosage and type).

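### The SAP names mean pain but tests it with Mann-Whitney and plans no estimate or interval, so the p-value may not answer the question about the mean

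*SAP*

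**What the plan says.** Pain is in the trial's title and its aim. The Protocol, under Research design, describes a trial "designed to look for a statistical difference in pain and rise of inflammatory markers post operatively", and names no effect measure. Under Observations it collects a "pain score out of 10 according to patient perception recorded at 6hr, 12hr and 24hr post-op", and after discharge a "pain score out of 10 according to patient perception recorded on 7th day post-op". That makes four time points. Under Sample size: "A convenient sample of 100 participants is decided, divided into 50 for each study group". For the analysis, the Protocol refers to a separate file.

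That file, the SAP, is a single paragraph. Its whole text on pain is "The mean intensity of pain was analyzed using Mann-Whitney U test". The threshold for every test follows: "value was set at 0.05 to consider results significant". No median, mean difference, Hodges-Lehmann shift, probability measure or confidence interval is named for pain. The SAP also does not say how the four time points are handled. Sidedness is stated only for operative time, insufflation time and hospital stay, which "were analyzed using Student's 2-tailed t-test".

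**The concern.** Mann-Whitney asks whether a patient in one arm tends to score lower than a patient in the other. That is a question about means only under extra conditions, the simplest being that one arm's distribution is the other's moved along the scale. The SAP states no such condition. As written, it names one quantity for a headline outcome and attaches the p-value to another.

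Two things are at stake. First, if the arms differ in skewness or in the share with severe pain, the rank test and the mean can lead to different conclusions. The difference can go either way: a significant rank test with no difference in means, or a real difference in means that the rank test tends to miss. Second, even where the two agree, the plan does not tell the reader how much pain is reduced on the 10-point scale, or how precisely that is known.

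**Working it through.** **Inputs from the documents:** 50 per arm; scores from 0 to 10; significance level 0.05. **Assumed:** whole-number scores, two-sided testing for Mann-Whitney, and every score distribution below, because the documents give no pain mean, SD or shape. The sample size is a convenience figure with no calculation behind it, so there is no plan figure to reproduce.

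**Step 1. One data set, by hand.** Take 50 scores per arm:

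- Low pressure: 1 (6 patients), 2 (28), 3 (3), 8 (9), 9 (4). Sum 179, mean 179/50 = 3.58, median 2, variance 8.249.
- Standard pressure: 1 (2), 2 (8), 3 (20), 4 (14), 5 (6). Sum 164, mean 164/50 = 3.28, median 3, variance 1.022.

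Mann-Whitney: count the pairs in which the low-pressure score is higher, plus half of ties.

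- U = 6×1 + 28×6 + 3×20 + 13×50 = 884 out of 50×50 = 2,500 pairs.
- Probability that the low-pressure score is higher = 884/2,500 = 0.354, so the probability of less pain under low pressure is 0.646.
- Tie-corrected variance = (2,500/12) × (101 − 62,988/9,900) = 19,716, SD 140.4.
- z = (1,250 − 884 − 0.5)/140.4 = 2.60, p = 0.009, favouring low pressure.

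Mean difference:

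- 3.58 − 3.28 = +0.30, favouring standard pressure.
- SE = √((8.249 + 1.022)/50) = 0.431, t = 0.30/0.431 = 0.70, Welch p = 0.49.
- 95% CI: 0.30 ± 2.00×0.431 = −0.56 to +1.16.

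So the two can disagree even in direction. This example is built to show it; one arm has a separate cluster at 8 and 9.

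**Step 2. How often, by shape.** Simulated trials with 50 per arm, 20,000 per row for the first four rows and 10,000 for the last two. Mann-Whitney (MW) is tie-corrected. The last column is the share of trials in which MW is significant while the mean difference is zero or opposite in direction.

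| Assumed distributions (low v standard) | Means | SDs | MW significant | Welch significant | Zero or opposite direction |
|---|---|---|---|---|---|
| Identical shape, no effect | 3.29 v 3.29 | 1.85 v 1.85 | 4.8% | 4.8% | 0% |
| Pure one-point shift | 3.29 v 4.29 | 1.85 v 1.85 | 78.8% | 76.4% | 0% |
| Strong skewness in one arm | 3.20 v 3.15 | 2.46 v 1.01 | 82.5% | 5.1% | 37.6% |
| Milder skewness in one arm | 3.13 v 3.19 | 2.58 v 1.35 | 35.1% | 6.2% | 0.3% |
| Symmetric, spread only (rounded normal) | 4.00 v 4.05 | 1.23 v 2.38 | 5.9% | 4.9% | 0% |
| Beta-binomial, equal means | 3.0 v 3.0 | 1.5 v 2.5 | 11.0% | 5.3% | 0% |

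The first four rows use these percentages at scores 0 to 10:

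- Rows 1 and 2: 5, 10, 20, 25, 18, 10, 6, 3, 2, 1, 0, with the standard arm moved up one point in row 2.
- Row 3: low 0, 10, 60, 10, 0, 0, 0, 5, 10, 5, 0; standard 0, 5, 20, 40, 25, 10, then zeros.
- Row 4: low 10, 18, 25, 17, 8, 4, 3, 4, 5, 4, 2; standard 2, 8, 20, 30, 25, 10, 4, 1, then zeros.

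**Step 3. Fewer patients with severe pain.** Suppose low pressure cuts the share with severe pain from 30% to 10% and mean pain falls from 4.0 to 3.0. If the two groups' own means are unchanged, 0.7m + 0.3s = 4.0 and 0.9m + 0.1s = 3.0, so s − m = 1.0/0.2 = 5, m = 2.5 and s = 7.5. Mann-Whitney is significant in about 42% of such trials and Welch in about 59%. Here the rank test loses power for a benefit that the mean reflects.

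**Step 4. What a missing interval hides.** If the SD is 1.5 to 2.5 points in both arms (assumed), the 95% CI for a mean difference has half-width 1.98 × SD × √(2/50) = 0.40 × SD, that is ±0.6 to ±1.0 points on the 10-point scale.

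**The case against.** **The test is a standard one.** A patient-perceived 0-10 score is bounded, discrete and often treated as ordinal. This stands: nothing here says that Mann-Whitney is the wrong test.

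**The harm is inferred.** A reader might infer that the trial will report a mean difference beside a Mann-Whitney p-value. Neither document says so. The Protocol asks only for a difference in pain, which a rank test addresses, and the SAP uses the word mean freely for other outcomes too. This stands as a limit on the claim. It does not remove the mismatch, because the one sentence that defines the pain analysis still names a mean.

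**The large percentages need particular shapes.** A reader might infer that any difference in SD between arms causes trouble. It does not: a symmetric difference in spread leaves the two tests almost level, a beta-binomial difference gives 11.0% v 5.3%, and opposite directions are rare outside extreme shapes. With means 4 v 3 and SDs 2.2 v 1.8 (beta-binomial) the tests detect the effect 63.9% v 69.5% of the time, which is close. This also stands.

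**No estimate is named for any outcome in the SAP,** so the omission is not special to pain. True, but pain is a headline outcome, and here the named quantity and the test also differ.

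**Adding a second test would make things worse.** Two p-values at each of four time points would be 4×2 = 8 pain tests at 0.05, with none named primary. This is right, and the fix asks for only one.

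**Conclusion.** The point holds in a limited form. The SAP names mean pain, tests something that equals a comparison of means only under unstated conditions, and plans no estimate or interval. The Protocol does not repair this.

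The possible size ranges from negligible to large, depending on a distribution that the documents do not give. Under a pure shift or a symmetric difference in spread the conclusion is nearly the same either way. With skewness in one arm, or a change in the share with severe pain, the rates of significance can differ by roughly 17 percentage points (59% v 42%) to 29 (35.1% v 6.2%), and by more in extreme shapes. The claim is therefore that the p-value and the mean can lead to different conclusions, not that they will. Mann-Whitney does have effect measures of its own; the plan simply names none.

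The lack of an estimate and interval does not depend on any of these assumptions.

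**What to change.** At each pain time point (6 h, 12 h, 24 h and day 7), state one matched pair of test and estimate, by one of two routes:

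- **Keep Mann-Whitney.** Replace the reference to mean intensity with the quantity tested, and report the probability of less pain under low pressure, counting half of ties, with a 95% CI. A mean difference with a 95% CI may be added as description only, without a second p-value. Claim no difference in mean pain from the Mann-Whitney p-value.
- **Keep the mean.** Report the mean difference on the 0-10 scale with its Welch 95% CI and p-value. The SAP already uses Welch's test for the inflammatory markers.

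The cost is a change of wording in the SAP and one or two extra output lines per time point. No new data or patients are needed. Although the SAP is written in the past tense, the change can still be made, because it uses scores that the Protocol already collects.

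### The marker aim is a difference in rise, but the SAP compares levels with no baseline covariate or sampling time: precision may be lost, though the comparison is not biased

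*SAP*

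**What the plan says.** The Protocol states the marker aim twice, each time as a rise. In the Study Summary, patients are randomised and "then assessed post operatively for pain and rise of inflammatory markers". Research design describes a trial "designed to look for a statistical difference in pain and rise of inflammatory markers post operatively between interventional group" and standard care.

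Under Observations, the list of ten laboratory markers opens with "The following inflammatory markers are to be investigated" and gives no sampling time. The pre-operative items in that section are demographics and history; no marker is among them. Flow of study work says only that tubes are "labeled with patient name, MRM, date, and time of collection", which records when blood was drawn but sets no schedule. Pain is handled differently: Observations asks for a "pain score out of 10 according to patient perception recorded at 6hr, 12hr and 24hr post-op", plus a further score on day 7.

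The SAP, a single paragraph, says of the ten markers that their "levels were analyzed using Welch's t-test". It uses the same test a second time: "Subgroup analysis for the inflammatory markers was done to eliminate the effect of dexamethasone". Neither analysis names a time point, a change score or a baseline covariate.

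**The concern.** A rise is a within-patient quantity, the post-operative value minus the pre-operative one. A level is a single measurement. Welch's two-sample test can be run on either, and the SAP's word more naturally means the post-operative value alone.

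Two things are at stake. First, if pre-operative values exist, a level-only comparison leaves differences between patients that were there before surgery in the noise of the estimate. That matters for one of the trial's two stated aims, in a trial whose size was chosen for convenience. Second, post-operative values alone cannot show that any patient's marker went up, so a report phrased in terms of rise would say more than the test supports. The missing time point compounds both, because neither a t-test nor a regression is fully defined until the measurement is named.

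**Working it through.** **Inputs from the documents.** 100 patients, 50 per arm (Protocol, Sample size; 50 + 50 = 100, which adds up). Significance level 0.05 (SAP). There is no power calculation to reproduce, and no SD, effect size or correlation is given.

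**Assumed inputs.** Two-sided testing; SD 1 before and after surgery; pre/post correlation r of 0, 0.3, 0.5 or 0.7; true difference 0.566 SD, the size that gives the unadjusted t-test 80% power at 50 per arm.

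**Step 1: do level and rise have the same target?** Write Y for the post-operative and B for the pre-operative mean, in arms 1 and 0.

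(Y1 − B1) − (Y0 − B0) = (Y1 − Y0) − (B1 − B0)

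Randomisation makes the expectation of B1 − B0 zero, so at a common time both comparisons estimate the same quantity. Simulation agrees: with a true difference of 0.5 SD, level, change and adjusted estimates all averaged 0.50 (8,000 trials per setting). With no true difference, type I error was 4.6% to 5.2% for Welch on levels and 4.3% to 4.7% for the adjusted model with HC3 errors. On the log scale the same identity applies to fold rise.

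**Step 2: precision if a baseline exists.** The standard error of the level comparison is √(2/50) = 0.200. With baseline adjustment it is 0.200 × √(1 − r²). The difference detectable with 80% power is (1.960 + 0.842) × SE by the normal approximation, which gives 0.560 for levels; the t distribution gives 0.566.

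| r | SE, level | SE, adjusted | Detectable, level | Detectable, adjusted |
|---|---|---|---|---|
| 0.3 | 0.200 | 0.200 × √0.91 = 0.191 | 0.560 | 0.535 |
| 0.5 | 0.200 | 0.200 × √0.75 = 0.173 | 0.560 | 0.485 |
| 0.7 | 0.200 | 0.200 × √0.51 = 0.143 | 0.560 | 0.400 |

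**Step 3: power by simulation, normal data** (40,000 trials per setting, effect 0.566 SD).

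| r | Level | Change score | Adjusted, HC3 |
|---|---|---|---|
| 0 | 80% | 51% | 79% |
| 0.3 | 80% | 66% | 82% |
| 0.5 | 80% | 80% | 89% |
| 0.7 | 80% | 95% | 97% |

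A change score is not the remedy: below r = 0.5 it does worse than the level alone. At these correlations the adjusted model stays within about 1 point of the level or improves on it.

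**Step 4: skewed markers.** Lognormal data, assumed log-SD 1, same effect on the log scale, 50 per arm.

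| r (log scale) | Raw Welch | Raw adjusted, HC3 | Log Welch | Log adjusted |
|---|---|---|---|---|
| 0.3 | 60–62% | 61% | 79–81% | 82% |
| 0.5 | 60–62% | 65% | 79–81% | 89% |
| 0.7 | 60–62% | 79% | 79–81% | 97% |

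Here the choice of scale does as much as adjustment or more, and it needs no baseline sample. Type I error of the raw adjusted model stayed at about 4% to 5%.

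**Step 5: why HC3.** Welch's test protects against unequal variances, and a replacement should too. In an assumed dexamethasone subgroup of 15 v 30 with SD 2 v 1 and r = 0.5, type I error was 11.7% for ordinary ANCOVA, 5.3% with HC3 errors and 5.3% for Welch.

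**The case against.** The strongest case for leaving the SAP alone is that Welch's test on levels is valid. The stated aim is a difference between arms, and Step 1 shows that a level comparison at a common time estimates it. The documents show no pre-operative sample, so the remedy may rest on data that do not exist. Every power figure rests on assumed inputs. The past tense of the SAP suggests that the results may already be known.

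All of that stands. It limits the point to precision and wording but does not remove it. Where a baseline exists, the adjusted model is better and cheap. Where none exists, the limit on what can be said about a rise still applies.

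A reader might infer more than the documents support:

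- *That the SAP tests the wrong quantity, so without a baseline the trial can conclude only about levels.* Step 1 rules this out. The between-arm conclusion stands; what is missing is evidence of a rise within patients.
- *That chance baseline imbalance biases the result.* An imbalance above 0.2 SD occurs in about 16% of trials in each direction, and at r = 0.3, 0.5 and 0.7 it shifts the level-only estimate by about 16%, 27% and 38% down or up. These shifts cancel on average, and the ordinary confidence interval already allows for them.
- *That the 11.7% error in Step 5 is a defect of the SAP.* It belongs to ordinary ANCOVA, which the SAP does not plan.
- *That no pre-operative blood was drawn.* The documents are silent. The word rise implies a baseline, but no section schedules one.

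**Conclusion.** The point holds as a matter of precision and of what may be claimed. The aim is worded as a rise; the analysis is of levels at an unstated time, without a baseline covariate. Bias and inflated type I error are not at issue.

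If a baseline exists, and on a scale where the data are near normal, adjustment is worth roughly 2 points of power at a correlation of 0.3, 9 at 0.5 and 17 at 0.7; at zero correlation it costs about 1. These gains should not be read as expected values for this trial. They rest on an assumed effect and correlation, and for strongly skewed markers kept on the raw scale there is almost no gain at 0.3 and only a few points at 0.5. If no baseline exists there is no gain from adjustment, and the consequence is one of wording. The change is advisable rather than essential, with medium confidence because the documents do not show whether a baseline was taken.

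**What to change.** 1. **If pre-operative samples were drawn:** state the pre-operative and post-operative sampling times and name one main post-operative time; the tube labels allow the times actually used to be checked. Replace Welch's test for each marker, overall and in the dexamethasone subgroup, with linear regression of the post-operative value at that time on arm and the patient's pre-operative value, using HC3 standard errors. Report the adjusted difference and 95% CI. For markers expected to be right-skewed, such as CRP and the cytokines, name the log scale in advance as the main scale (both values logged) and report ratios of geometric means.
2. **If no pre-operative sample exists:** keep Welch's test at one named time. The between-arm conclusion stands, but the report should not claim that markers rose within patients.
3. **If results have been seen:** label the adjusted analysis post hoc and report it beside the Welch result.

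**Cost.** With a baseline, a few lines of SAP text and one regression per marker, after checking that the software offers HC3 errors. Without one, wording only. No new assays are needed in either case. The downsides are slightly more analysis work, about 1 point of power if the correlation is near zero (79% v 80%; in an assumed 15 v 30 subgroup, about 38% v 41%), and log-scale results that read as ratios, not differences.
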